3. DESCRIPTION OF DESIGN AND TRIAL POPULATION

3.1 OVERALL TRIAL DESIGN AND PLAN

This study will explore the relative bioavailability, safety, and tolerability following a subcutaneous (SC) injection of BI 655130 at different dose strengths, injection volumes, and injection sites:

- One SC injection of periumbilical (Dose Group 1)
- Two SC injections of each periumbilical left and right (Dose Group 2)
- Two SC injections of each periumbilical left and right (Dose Group 3)
- One SC injection of in the thigh (Dose Group 4)

The total dose in Dose Group 1, 2, and 4 is of BI 655130 and the total dose in Dose Group 3 is of BI 655130.

The study will be conducted in a single-dose, open-label, matched-group design. The exposure in Dose Group 1 will be used as reference to assess the relative bioavailability of Dose groups 2 - 4. For details refer to [Section 4.1](#).

The study will start with Dose Group 1 and 2. After completion of treatment of the first two dose groups, the study will continue with Dose Group 3 and 4. At any time during the ongoing study, further dosing will be stopped in case of safety and tolerability concerns based on the pre-specified trial-specific stopping criteria ([Section 3.3.4.2](#)).

The Dose Group 3 will follow a staggered administration with treatment of 6 subjects (cohort A) in the first week and the remaining subjects (cohort B) from Week 2.

A documented Safety Review of Dose Group 1 and 2 at least 10 days after last dosing in Dose Group 2 must take place prior to continue the study with Dose Groups 3 and 4. An unscheduled safety review meeting can be requested anytime for any reasonable cause by the Principal Investigator (or an authorised deputy) or the sponsor of the study, e.g. because of any unforeseen adverse events. Continuation of the study will only be permitted if no safety concerns exist in the opinion of the Principal Investigator (or an authorised deputy) and the trial clinical monitor (or an authorised deputy). In addition, at least 8 evaluable subjects in each of the Dose Group 1 and 2 are required to decide about continuation with the remaining dose groups.

The minimum data set for review consists of the following data:

- AEs (including clinically relevant findings from ancillary safety testing listed below)
(Note: AEs may be ongoing at the time of Safety Reviews and AE information may be subject to change prior to Database Lock)
- Vital signs
- Clinical laboratory tests
- Check of criteria for stopping subject treatment as per [Section 3.3.4.1](#)

Proprietary confidential information © 2019 Boehringer Ingelheim International GmbH or one or more of its affiliated companies

The decision to escalate the dose will be made jointly by the Principal Investigator (or an authorised deputy) and the trial clinical monitor (or an authorised deputy) after in-depth analysis of all available safety data, especially SAEs (if occurred), AEs and out-of-range laboratory results (if considered clinically significant). Safety Reviews can be conducted face-to-face or by video/telephone conference. The trial clinical monitor or a delegate is responsible for organisation and minutes of the reviews. Minutes will be signed off by the Principal Investigator (or an authorised deputy) and filed in the ISF and TMF.

An overview of all relevant trial activities is provided in the [Flow Chart](#). For visit schedule and details of trial procedures at selected visits, refer to [Sections 6.1](#) and [6.2](#), respectively.

3.2 DISCUSSION OF TRIAL DESIGN, INCLUDING THE CHOICE OF CONTROL GROUP

The study will be conducted according to a single-dose, open-label design with matched groups.

The resulting group sizes (see [Section 7.6](#)) are considered to be sufficient for the exploratory evaluation of pharmacokinetics. The assignment of matched healthy volunteers is a useful method to control for other factors which may influence the pharmacokinetics of BI 1467335 in a renal impaired population.

The open-label treatment is not expected to bias results, since the primary endpoints are derived from measurement of plasma concentrations of the analytes provided by a bioanalytical laboratory. It is also considered sufficiently accurate as the trial observations are objective (PK, laboratory) and over-reporting of AEs is unlikely.

No placebo group is included because the study is open-label with a focus on PK. Local tolerability is an additional objective and will remain relevant in case of dose limiting local AEs, whether placebo controlled or not. The systemic tolerability of BI 655130 has already been evaluated up to MRD, resulting in a far higher exposure compared to the expected exposure of the current study.

3.3 SELECTION OF TRIAL POPULATION

It is planned that 48 healthy male and female subjects (12 in each dose group) will enter the study. They will be recruited from the volunteers' pool of the trial site. Healthy subjects assigned to Dose Groups 2 - 4 will be matched on an individual level for gender and body weight ($\pm 10\%$) to subjects assigned to Dose Group 1 (perumbilical injection).

A log of all subjects enrolled into the trial (i.e. having given informed consent) will be maintained in the ISF at the investigational site irrespective of whether they have been treated with investigational drug or not.

3.3.1 Main diagnosis for study entry

The study will be performed in healthy subjects.

3.3.2 Inclusion criteria

Subjects will only be included into the trial, if they meet the following criteria:

1. Healthy male or female subjects according to the investigator's assessment, based on a complete medical history including a physical examination, vital signs (BP, PR), 12-lead ECG, and clinical laboratory tests
2. Age of 18 to 50 years (incl.)
3. BMI of 19.0 to 29.9 kg/m² (incl.)

Proprietary confidential information © 2019 Boehringer Ingelheim International GmbH or one or more of its affiliated companies

4. Signed and dated written informed consent prior to admission to the study in accordance with ICH-GCP and local legislation
5. Male subjects, or female subjects who meet any of the following criteria starting from at least 30 days before the first administration of trial medication and until 30 days after trial completion:
 - Use of adequate contraception, e.g. any of the following methods *plus* condom: implants, injectables, combined oral or vaginal contraceptives, intrauterine device
 - Sexually abstinent
 - A vasectomised sexual partner (vasectomy at least 1 year prior to enrolment)
 - Surgically sterilised (including hysterectomy)
 - Postmenopausal, defined as at least 1 year of spontaneous amenorrhea (in questionable cases a blood sample with simultaneous levels of FSH above 40 IU/L and estradiol below 30 ng/L is confirmatory)

3.3.3 Exclusion criteria

Subjects will not be allowed to participate if any of the following general criteria apply:

1. Any finding in the medical examination (including BP, PR or ECG) is deviating from normal and judged as clinically relevant by the investigator
2. Repeated measurement of systolic blood pressure outside the range of 90 to 140 mmHg, diastolic blood pressure outside the range of 50 to 90 mmHg, or pulse rate outside the range of 45 to 90 bpm
3. Any laboratory value outside the reference range that the investigator considers to be of clinical relevance
4. Any evidence of a concomitant disease judged as clinically relevant by the investigator
5. Gastrointestinal, hepatic, renal, respiratory, cardiovascular, metabolic, immunological or hormonal disorders
6. Diseases of the central nervous system (including but not limited to any kind of seizures or stroke), and other relevant neurological or psychiatric disorders
7. History of relevant orthostatic hypotension, fainting spells, or blackouts
8. Chronic or relevant acute infections
9. History of relevant allergy or hypersensitivity (including allergy to the trial medication or its excipients)
10. Use of drugs within 30 days prior to administration of trial medication if that might reasonably influence the results of the trial (incl. QT/QTc interval prolongation)
11. Participation in another trial where an investigational drug has been administered within 60 days prior to planned administration of trial medication, or current participation in another trial involving administration of investigational drug
12. Smoker (more than 10 cigarettes or 3 cigars or 3 pipes per day)
13. Inability to refrain from smoking on specified trial days
14. Alcohol abuse (consumption of more than 20 g per day for females and 30 g per day for males)

15. Drug abuse or positive drug screening
16. Blood donation of more than _____ within 30 days prior to administration of trial medication or intended donation during the trial
17. Intention to perform excessive physical activities within one week prior to administration of trial medication up to 4 weeks after administration
18. Inability to comply with dietary regimen of trial site
19. A marked baseline prolongation of QT/QTc interval (such as QTc intervals that are repeatedly greater than 450 ms in males or repeatedly greater than 470 ms in females) or any other relevant ECG finding at screening
20. A history of additional risk factors for Torsades de Pointes (such as heart failure, hypokalemia, or family history of Long QT Syndrome)
21. Subject is assessed as unsuitable for inclusion by the investigator, for instance, because considered not able to understand and comply with study requirements, or has a condition that would not allow safe participation in the study

Female subjects will not be allowed to participate if any of the following applies:

22. Positive pregnancy test, pregnancy or plans to become pregnant up to study completion
23. Lactation

In addition, the following trial-specific exclusion criterion applies:

24. Previous use of the trial medication

For study restrictions, refer to [Section 4.2.2](#).

3.3.4 Removal of subjects from therapy or assessments

3.3.4.1 Removal of individual subjects

This study is a single dose study, therefore removal of subjects from study medication after dosing is not applicable.

An individual subject is to be removed from further assessments if:

1. The subject withdraws consent for trial treatment or trial participation, without the need to justify the decision
2. The subject needs to take concomitant drugs that interfere with the investigational product or other trial medication
3. The subject is no longer able to participate for other medical reasons (such as pregnancy, surgery, adverse events, or diseases)
4. An AE or clinically significant laboratory change or abnormality occurred that the investigator judges to warrant discontinuation from further assessments. This may include cases of sustained symptomatic hypotension (BP <90/50 mmHg) or hypertension (BP

Proprietary confidential information © 2019 Boehringer Ingelheim International GmbH or one or more of its affiliated companies

>180/100 mmHg) or of clinically relevant changes in ECG requiring intervention as well as unexplained liver enzyme elevations at any time during the trial

5. The subject shows an elevation of AST and/or ALT \geq 3-fold ULN combined with an elevation of total bilirubin \geq 2-fold ULN (measured in the same blood sample) and/or marked peak aminotransferase (ALT and/or AST) elevations \geq 10-fold ULN and/or needs to be followed up according to the 'DILI checklist' provided in the ISF.

In addition to these criteria, the physician may discontinue subjects at any time based on his or her clinical judgment.

A subject can also be removed from the trial if eligibility criteria are being violated or if the subject fails to comply with the protocol (for instance, by non-adherence to dietary rules, or non-attendance at study assessments).

If a subject is removed from or withdraws from the trial prior to administration of trial medication, the data of this subject will not be entered in the case report form (CRF) or trial database and will not be reported in the clinical trial report (CTR). If a subject is removed from or withdraws from the trial after administration of trial medication, this will be documented and the reason for discontinuation must be recorded in the CRF. In this case, the data will be included in the CRF/trial database and will be reported in the CTR. At the time of discontinuation a complete end of trial examination will be performed if possible and the information will be recorded in the CRFs. If the discontinuation occurs before the end of the REP (i.e., 16 weeks, see [Section 1.2.5](#)), the discontinued subject should if possible be questioned for AEs and concomitant therapies at or after the end of the REP in order to ascertain collection of AEs and concomitant therapies throughout the REP, if not contrary to any consent withdrawal of the subject. These discontinuations will be discussed in the CTR.

If it is known that a subject becomes pregnant during the trial, the subject has to be removed from the trial. The subject is to be followed until she has given birth or until the end of pregnancy. The subject's data are to be collected until the end of the trial (last visit of last subject) and reported in the CTR. For reporting of pregnancy and all related events refer to [Section 5.2.2](#).

3.3.4.2 Discontinuation of the trial by the sponsor

Boehringer Ingelheim reserves the right to discontinue the trial overall or at a particular trial site at any time for any of the following reasons:

1. New toxicological findings or serious adverse events invalidate the earlier positive benefit-risk-assessment. More specifically, the trial will be terminated if more than 50% of the subjects show drug-related and clinically relevant adverse events of moderate or severe intensity, or if at least one drug-related serious adverse event is reported that is considered to be unacceptable
2. The expected enrolment goals are not met
3. Violation of GCP, or the CTP, or the contract with BI by the trial site or investigator, disturbing the appropriate conduct of the trial
4. The sponsor decides to discontinue the further development of the investigational product

Proprietary confidential information © 2019 Boehringer Ingelheim International GmbH or one or more of its affiliated companies

5. Further dosing will be stopped if at least 2 subjects in one dose group show relevant individual QT prolongation, i.e. a QTc increase of greater 60 ms from baseline in connection with absolute QT or QTc greater than 500 ms, which has been confirmed by a repeat ECG recording

The investigator / the trial site will be reimbursed for reasonable expenses incurred in case of trial termination (except in case of the third reason).

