1.2.5 Clinical experience

In Phase I, BI 655130 has been evaluated in three clinical trials: a first-in-human (FIH) SRD trial [[c09985235-01](#)], an MRD trial [[c09105854-05](#)], and a recently completed relative bioavailability study exploring the pharmacokinetics as well as safety and tolerability of a newly developed SC formulation (1368-0003, [[c10896574-01](#)]).

FIH-Study (Trial 1368.1)

The FIH (first-in-human) trial [[c09985235-01](#)] explored safety, tolerability, pharmacokinetics, and pharmacodynamics of intravenously administered BI 655130 in healthy male subjects. Subjects received single ascending IV doses of up to body weight or placebo. Overall, the study included 78 male subjects with 58 subjects treated with BI 655130 and 20 subjects treated with placebo.

At preferred term level, the most frequently reported treatment-emergent AEs were nasopharyngitis (BI 655130: 12/58 subjects [20.7%]; placebo: 3/20 subjects [15.0%]), headache (BI 655130: 5/58 subjects [8.6%]; placebo: 3/20 subjects [15.0%]), influenza like illness (BI 655130: 4/58 subjects [6.9%]; placebo: 2/20 subjects [10.0%]), and diarrhea (BI 655130: 2/58 subjects [3.4%]; placebo: 2/20 subjects [10.0%]).

There were two AEs of moderate intensity, both considered not related to the study drug, (injection site hematoma and headache); all remaining AEs were of mild intensity. There were no relevant changes compared to placebo for laboratory safety, including clinical chemistry, hematology, coagulation parameters, and urinalysis. Deaths, serious AEs, and protocol-specified AEs of special interest were not reported in this trial. No clinically relevant changes were observed in 12 lead ECGs, vital signs, physical exams, and cardio-monitoring.

MRD study (Trial 1368.2)

Trial 1368.2 [[c09105854-05](#)] explored the safety, tolerability, pharmacokinetics, and pharmacodynamics of multiple rising intravenous doses of BI.

In total, 40 subjects entered this trial and were treated. The study consisted of a multiple dose part with four dose groups and a single dose arm

A total of 32 subjects were assigned to the MRD part. In each of the 4 dose groups 6 subjects received BI 655130 and 2 subjects received placebo. Additional 8 subjects entered the SD part of the trial with 6 subjects assigned to BI 655130 and 2 subjects assigned to placebo [[c18789185-01](#)].

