Based on studies in healthy subjects, no specific drug-related risks are anticipated. Nevertheless, the following safety measures are/will be applied in this study in order to minimize the risk for the healthy subjects:

Proprietary confidential information © 2019 Boehringer Ingelheim International GmbH or one or more of its affiliated companies

- The study will start with Dose Group 1 and 2 (perumbilical SC dose of of BI 655130). Provided no dose limiting AEs occurred as approved by the Principal Investigator (or an authorised deputy) and the trial clinical monitor (or an authorised deputy) after in-depth analysis of all available safety data up to Day 10 (see [Section 3.1](#)), the study will pursue with Dose Group 3 (perumbilical SC dose of of BI 655130) and Dose Group 4 (SC dose of of BI 655130 in the thigh). Dose Group 3 will be divided into 2 cohorts. In the first week, 6 subjects will be treated. There will be an interval of at least 1 week after start of dosing in the first cohort before start of dosing of the second cohort of Dose Group 3.
- At any time during the ongoing study, further dosing will be stopped in case of safety and tolerability concerns based on the criteria defined in [Section 3.1](#).
- Monitoring of ECG, vital signs, and extensive safety laboratory testing ([Table 5.2.3:1](#)) is conducted throughout the study.
- After dosing, the subjects will stay at the site for at least 48 hours.
- BI 655130 will be administered in a hospital setting and subjects will be under close medical observation during their hospitalisation (see [Section 6.2](#)), as well as after their discharge and until the end of observation period. Safety will be closely monitored during site visits for both expected and unexpected adverse events.

Currently there are no data available to suggest interactions of BI 655130 [[c03320877-04](#)].

Although rare, a potential for drug-induced liver injury (DILI) is under constant surveillance by sponsors and regulators. Therefore, this study requires timely detection, evaluation, and follow-up of laboratory alterations in selected liver laboratory parameters to ensure subjects' safety, see also [Section 5.2.2.1](#), adverse events of special interest.

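### The AE-rate stopping rule has no dose-group denominator, and no review is scheduled between the two cohorts of the highest-dose group

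*Protocol*

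**What the plan says.** Protocol Section 3.1 makes the discontinuation criteria of Section 3.3.4.2 the operative rule for dosing: "further dosing will be stopped in case of safety and tolerability concerns based on the pre-specified trial-specific stopping criteria". Section 2.3 points to the same place by way of Section 3.1.

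In that list, item 1 is the only criterion that acts on the frequency of non-serious AEs: "the trial will be terminated if more than 50% of the subjects show drug-related and clinically relevant adverse events of moderate or severe intensity". It gives no dose group, cohort or treated-so-far base. Item 5 of the same list does give a unit: "Further dosing will be stopped if at least 2 subjects in one dose group show relevant individual QT prolongation". The SAP does not define a denominator for item 1.

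On numbers and order, Section 3.3 states: "It is planned that 48 healthy male and female subjects (12 in each dose group) will enter the study". Under Section 3.1, Dose Groups 1 and 2 are dosed first, then Dose Groups 3 and 4. The one scheduled review lies between those two stages: "A documented Safety Review of Dose Group 1 and 2 at least 10 days after last dosing in Dose Group 2 must take place".

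Within Dose Group 3, Section 3.1 adds a stagger: "The Dose Group 3 will follow a staggered administration with treatment of 6 subjects (cohort A) in the first week", with the remaining subjects from Week 2. Section 2.3 describes the gap by time alone: "There will be an interval of at least 1 week after start of dosing in the first cohort". Neither section attaches a review to it.

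**The concern.** Dose Group 3 receives the highest dose and is the only group split into cohorts. The purpose of a 6 + 6 split is to learn from the first six before exposing the other six. Moderate, non-serious, drug-related AEs, including injection-site reactions, are what a rate rule should catch there.

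If item 1 is counted over the whole trial, 24 earlier subjects dilute whatever happens in cohort A. If it is counted per group, the answer depends on a further unwritten choice between planned and treated subjects. The same cohort A data could therefore lead two reasonable readers to opposite decisions about cohort B, and no scheduled meeting exists at which the question must be settled.

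**Working it through.** The protocol gives no operating figure for this rule, so there is none to reproduce.

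**Inputs.** Section 3.3: 48 subjects, 12 per group. Section 3.1: Dose Groups 1 and 2 (24 subjects) before Dose Groups 3 and 4 (24 subjects); cohort A has 6 subjects. Section 3.3.4.2 item 1: the share must strictly exceed 50%. A qualifying AE below means one that meets item 1's description.

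**Step 1: all 6 of cohort A affected, nobody else.**

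| Denominator | Share | Above 50%? |
|---|---|---|
| 48 planned in the trial | 6/48 = 12.5% | no |
| 42 treated (24 + 6 + all 12 of Dose Group 4) | 6/42 = 14.3% | no |
| 30 treated (24 + 6, Dose Group 4 not started) | 6/30 = 20.0% | no |
| 12 planned in Dose Group 3 | 6/12 = 50.0% | no |
| 6 treated in Dose Group 3 | 6/6 = 100% | yes |

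Only the last reading stops dosing.

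**Step 2: all 12 of Dose Group 3 affected, nobody else.** The share is 12/36 = 33.3% with Dose Group 4 not started, or 12/48 = 25.0% with Dose Group 4 dosed and event-free. To exceed 50%, 7 further affected subjects are needed in the first case (19/36 = 52.8%) and 13 in the second (25/48 = 52.1%).

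**Step 3: how many earlier events would let cohort A trigger the trial-wide rule?** With k of the first 24 affected and Dose Group 4 not started, (k + 6)/30 > 0.5 requires k > 9, so k is at least 10 (16/30 = 53.3%). At k = 13 the rule would already have been met by the first 24 alone (13/24 = 54.2%). A complete 6 of 6 in cohort A therefore changes the decision only when 10, 11 or 12 of the first 24 are already affected.

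**Step 4: a threshold inside cohort A.** The smallest count above half of six is 4 (4/6 = 66.7%). With X the number affected and p the true rate, P(X ≥ 4) = 15p⁴(1−p)² + 6p⁵(1−p) + p⁶. At p = 0.20 this is 0.01536 + 0.00154 + 0.00006 = 0.017. The rates below are assumed; the documents give none for this dose.

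| True rate p | P(at least 4 of 6) |
|---|---|
| 10% | 0.001 |
| 20% | 0.017 |
| 50% | 0.344 |
| 70% | 0.744 |
| 90% | 0.984 |

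**The case against.** The strongest reply is that item 1 is a backstop for ending the whole trial, listed under the sponsor's right to discontinue, and was never meant as a per-group pause. Other protections cover cohort B: the clause on an unacceptable drug-related SAE, the per-group QTc rule, and unscheduled reviews that the Principal Investigator or sponsor may request. Section 3.1 also permits continuation only if the Principal Investigator and the trial clinical monitor see no safety concern. Six of six subjects with moderate drug-related AEs would plainly be one. Section 2.3 adds that exposure at the earlier top SC dose was about 6-fold below the maximum reached intravenously, and that the new maximum SC dose is not expected to exceed exposures already tested.

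Much of this stands. A reader might infer that the protocol would let cohort B be dosed whatever happened in cohort A. It would not: the no-safety-concern condition is a written bar. But it works by judgement, and the SAE and QTc criteria respond to other events. Nor is item 1 only a termination clause, since Section 3.1 uses the same list to stop further dosing. The exposure argument is systemic and does not cover injection-site reactions, while Section 3.2 itself contemplates dose-limiting local AEs.

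A reader might also take an event-free Dose Group 1 and 2 to be the expected case. The documents do not show that. Section 1.2.5 says of the first-in-human trial: "There were two AEs of moderate intensity, both considered not related to the study drug". For the earlier SC trial, however, the transient redness and swelling describe local findings only. Systemic AEs there are said not to have been severe, which leaves moderate ones open. The multiple-dose trial reports drug-related AEs in 16.7% to 66.7% of subjects across its placebo and active groups, without giving their intensity.

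**Conclusion.** The point holds as an undefined denominator plus a missing scheduled check. Read trial-wide after 24 event-free subjects, the only written rate rule for non-serious AEs reaches at most 20.0% on cohort A and 33.3% on all of Dose Group 3 (Dose Group 4 not started in either case). It cannot be relied on to protect cohort B. The per-group reading is open but unwritten, and gives 50.0% or 100% for the same data.

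A stronger inference is tempting: that after an event-free first stage the rule can never be met, because 24/48 is exactly 50.0%. That is true only with exactly 24 + 24 subjects, no early event and no replacement. One early event gives 25/48 = 52.1%. One fewer subject in the first stage gives 24/47 = 51.1%. One added subject in Dose Groups 3 and 4, which Section 3.3.5 allows by replacement, gives 25/49 = 51.0%. At an assumed 10% rate, the chance of no event in the first 24 is 0.9²⁴ = 8%. The insensitivity to Dose Group 3 alone does not depend on that coincidence.

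The counts assume planned group sizes; the probabilities rest on assumed rates. This is a cheap safety improvement. It does not affect the pharmacokinetic comparisons.

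**What to change.** Keep the trial-wide termination clause and make two additions.

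- **Section 3.1:** a documented check of the cohort A safety data, including local tolerability, at the existing one-week point and before cohort B is dosed.
- **Section 3.3.4.2:** if at least 4 of the 6 cohort A subjects have qualifying AEs (more than half of those treated), dosing of cohort B is paused pending joint review by the Principal Investigator and the trial clinical monitor.

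The threshold should be applied once, at that check. If it were left open to any dose group and re-checked after each subject up to the eleventh, the chance of a false pause at a true 20% rate would rise to about 4.0% per group. A matching clause for a completed group would do nothing, because no dosing would remain to stop.

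The cost is one sentence and one clause. No subject, visit or sample is added: the Flow Chart already schedules AE and local-tolerability queries on each of Days 1 to 8. If cohort A is dosed over several days of its week, the latest subjects will contribute fewer days to the check. The price is a needless pause with probability 0.1% at a true rate of 10% and 1.7% at 20% (assumed rates), and a pause for review does not end the trial.
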